## **DESIGN**

This study is designed as a prospective, multicenter, randomized, single-blind (participant), parallel-design, superiority, confirmatory trial. It aims to evaluate the efficacy and safety of a CBT based digital therapeutics, in reducing psychological and physical functional impairments caused by subjective tinnitus. Participants will be randomly assigned to either the intervention group using CBT based digital therapeutics or the control group receiving conventional CBT educational materials. The trial will assess changes in Tinnitus Handicap Inventory (THI) scores and other relevant outcomes over a period of 6 weeks.

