## **METHODS**

Participants are selected based on criteria including being aged 19 or older, having chronic tinnitus for more than three months, a THI score between 18 and 77, and the ability to use internet and applications. Exclusion criteria include objective tinnitus, middle ear infections, and other psychiatric conditions. The intervention involves using CBT based digital therapeutics, while the control group receives conventional CBT educational materials. The trial evaluates changes in THI scores and other relevant outcomes over six weeks.

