## **STATISTICAL ANALYSIS PLAN**

Statistical tests are conducted at a significance level of 5% or less, using two-sided tests. Descriptive statistics for continuous variables include mean, standard deviation, median, minimum, and maximum, while categorical variables are summarized by frequency and percentage. If data do not meet the assumption of normality, non-parametric methods like the Wilcoxon signed-rank test are used instead of parametric methods like the paired t-test, with normality assessed using the Shapiro-Wilk test, Kolmogorov-Smirnov test, or Q-Q plots. The latest version of R is used for statistical analysis, but other software can also be employed.

The analysis groups are defined as follows: the Full Analysis (FA) set includes all participants who have used the medical device at least once and undergone efficacy evaluation; the Per Protocol (PP) set consists of participants from the FA set who completed the trial without major protocol deviations; and the Safety Analysis Set includes all participants who have used the medical device at least once. Demographic information collected for the FA set includes age, height, weight, gender, smoking status, and alcohol consumption.

The primary efficacy variable is the change in Tinnitus Handicap Inventory (THI) total score from baseline to 6 weeks, analyzed using ANCOVA to compare groups while adjusting for baseline THI

and stratification factors. Secondary efficacy variables include changes in THI subscales, Tinnitus Functional Index (TFI), Visual Analog Scale (VAS) for negative emotions and thoughts, Beck Depression Inventory (BDI), and Beck Anxiety Inventory (BAI). Each secondary efficacy variable is analyzed using descriptive statistics at baseline and at 2, 4, and 6 weeks, with paired t-tests or Wilcoxon signed-rank tests used within groups and two-sample t-tests between groups. Repeated Measures ANOVA or linear mixed models can be used to assess changes over time.

Safety evaluation includes reporting adverse events, assessing vital signs using paired t-tests or Wilcoxon signed-rank tests, and analyzing physical and laboratory findings with paired t-tests for continuous variables and McNemar's test for categorical variables. Missing data are handled using the Last Observation Carried Forward (LOCF) method for the FA set, with available data used as is for other analyses.

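### LOCF is the only missing-data method for the FA set, with no stated assumption or sensitivity analysis, and can bias the week-6 THI comparison in either direction

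*Combined protocol and SAP*

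**What the plan says.** All the relevant rules are in the section STATISTICAL ANALYSIS PLAN unless noted.

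- **Primary variable:** "The primary efficacy variable is the change in Tinnitus Handicap Inventory (THI) total score from baseline to 6 weeks", compared between arms by ANCOVA with baseline THI and the stratification factors as covariates.
- **Missing data:** "Missing data are handled using the Last Observation Carried Forward (LOCF) method for the FA set", "with available data used as is for other analyses".
- **FA set:** "the Full Analysis (FA) set includes all participants who have used the medical device at least once and undergone efficacy evaluation". The evaluation is not said to be post-baseline. Every participant has a baseline THI, because METHODS makes "a THI score between 18 and 77" an entry criterion.
- **Visits:** "Each secondary efficacy variable is analyzed using descriptive statistics at baseline and at 2, 4, and 6 weeks". The secondary variables include the THI subscales, so THI totals at weeks 2 and 4 are implied but not stated.
- **Longitudinal models:** "Repeated Measures ANOVA or linear mixed models can be used to assess changes over time". This is optional, follows the text on secondary variables, and is tied neither to the primary comparison nor to missing data.

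The plan gives no missingness assumption, expected dropout rate or sensitivity analysis, and does not name the set used for the primary analysis. What follows assumes it is FA.

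**The concern.** LOCF fills in a missing week-6 THI with an earlier score, and the ANCOVA then treats it as observed. That is harmless only if scores stay flat after dropout, or if the resulting error is the same in both arms. The plan cannot presume the latter: one arm uses an app, with "the control group receiving conventional CBT educational materials", so both dropout and later change may differ.

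LOCF is often defended as conservative, but it is not reliably so. It can shrink a real effect, exaggerate one that is fading, or produce false rejections in favour of either arm. This bears on the single primary test of a confirmatory trial, and no planned sensitivity analysis would show which of these had happened.

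It is also open which score is carried. If a baseline score may be carried, that participant's change is fixed at exactly 0. The clause on other analyses does not settle whether a mixed model would use carried-forward or observed values.

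**Working it through.** The plan has no figure to reproduce: it gives no sample size, SD, dropout rate or trajectory. **All numerical inputs below are assumptions.**

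**Formula.** Let p_v be the share of an arm whose last THI is at visit v, and m_v that arm's mean THI change at visit v. If dropout is unrelated to the score, LOCF shifts the arm's mean week-6 change by Σ p_v × (m_v − m_6). The bias is the app sum minus the control sum; negative favours the app.

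**Assumed inputs.** THI SD is 13 at each visit, the correlation between any two visits is 0.65, and baseline mean is 45. Dropout is split equally between after week 2 and after week 4. An arm's shift is then its total dropout times the average of (m_2 − m_6) and (m_4 − m_6). Dropout is written app/control.

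**Closed-form results.**

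- *No true effect, both arms −4/−8/−12.* Average gap (8 + 4)/2 = 6.
  - 20/20%: 1.2 − 1.2 = 0
  - 10/15%: 0.6 − 0.9 = −0.3
  - 15/10%: 0.9 − 0.6 = +0.3
  - 30/10%: 1.8 − 0.6 = +1.2
  - 10/30%: 0.6 − 1.8 = −1.2
- *Flat after week 2.* All gaps are 0, so the bias is 0 whatever the dropout.
- *Growing effect, true −9 (app −6/−12/−18, control −3/−6/−9).* Gaps (12 + 6)/2 = 9 and (6 + 3)/2 = 4.5.
  - 20/20%: 1.8 − 0.9 = +0.9, estimate −8.1
  - 30/10%: 2.7 − 0.45 = +2.25, estimate −6.75
  - 10/30%: 0.9 − 1.35 = −0.45, estimate −9.45
- *Fading effect, true −3 (app −14/−12/−9, control flat at −6).* Gaps (−5 − 3)/2 = −4 and 0.
  - 20/20%: −0.8, estimate −3.8
  - 30/10%: −1.2, estimate −4.2
  - 10/30%: −0.4, estimate −3.4

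So at equal 20% dropout LOCF understates a growing effect and overstates a fading one.

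**Simulation, no true effect.** The analysis was ANCOVA of LOCF change on arm and baseline THI, with 100 per arm, two-sided 5% tests and 4000 trials per row. Paired figures are for dropout unrelated to the score / dropout more likely with a higher last score (logistic, slope 0.5 per SD, same average hazard).

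| Dropout, app/control | Bias (THI points) | False rejections favouring the app (nominal 2.5%) |
|---|---|---|
| 20/20% | 0.0 / 0.0 | 2.2% / 2.6% |
| 15/10% | +0.3 / +0.4 | 1.6% / 1.2% |
| 10/15% | −0.3 / −0.4 | 4.2% / 4.7% |
| 30/10% | +1.2 / +1.5 | 0.2% / 0.1% |
| 10/30% | −1.2 / −1.5 | 12.5% / 17.2% |

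At 30/10%, false rejections favouring control were 13.2% / 16.7%. In the growing and fading scenarios, score-dependent dropout moved the estimates by no more than about 0.4 points from the closed form.

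**Comparator.** Multiple imputation by arm (15 imputations, ANCOVA, Rubin's rules) was run under score-dependent dropout, 1200 trials per scenario. With no true effect and 100 per arm, bias was 0.03 with 4.6% total rejections at 10/30%, and 0.04 with 4.8% at 30/10%. For the fading effect (true −3) it gave −3.04 at 20/20% and −2.97 at 30/10%. These data are missing at random by construction, so this shows only that the method works under its stated assumption.

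**The case against.** The mechanism is not in dispute; the case on the other side concerns size and emphasis.

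- **The large figures need strong assumptions.** They combine threefold dropout imbalance with a decline still running at week 6. If the same 12-point fall levels off (−8/−11/−12), the average gap is (4 + 1)/2 = 2.5 and the bias at 10/30% is 0.25 − 0.75 = −0.5, or about −0.8 with score-dependent dropout. False rejections favouring the app drop to 5.1% / 8.7%. This stands.
- **The SAP's tests are two-sided.** At 10/15% the total rejection rate is about 5.4% / 5.9% against 5%, so mild imbalance does little harm. This also stands.
- **The per-protocol set offers a check.** With no true effect, 10/30% and score-dependent dropout, ANCOVA on completers has a bias of about +0.3 against −1.5 for LOCF, so a discrepancy could act as a warning. But the SAP neither assigns the primary ANCOVA to that set nor calls it a sensitivity analysis. It also excludes people for major deviations, which mixes two questions. This softens the point without answering it.
- **Carrying baseline is a strained reading.** If baseline counted as an efficacy evaluation, that FA condition would exclude nobody. This is fair: the wording needs settling, but the conclusion does not rest on it.
- **The document is condensed.** Fuller detail may exist elsewhere, but the missing-data rule in this one is explicit.

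**Conclusion.** The concern holds. LOCF is the only rule for the FA set, and nothing else in the plan protects the primary week-6 comparison. The bias depends on the arm difference in dropout share times unobserved later change, with score-dependent dropout adding to or offsetting it.

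Its size in this trial is unknown. Under the assumed inputs it runs from nil (equal dropout with parallel change, or flat scores) through 0.3 to 0.4 points at 10/15% dropout to 1.2 to 1.5 points at 10/30%. It can also appear with equal dropout when later change differs between arms. The conclusion assumes that FA is the primary set and that weeks 2 and 4 supply the carried scores.

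Because it affects the one confirmatory test, can act in either direction and is cheap to repair, it must be fixed before the analysis.

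**What to change.** Replace LOCF in the primary THI analysis with a method valid under missing at random, and state that assumption.

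1. **Primary method.** The smallest change is multiple imputation by arm, using THI total at baseline, week 2 and week 4 and the stratification factors, followed by the planned ANCOVA and Rubin's rules. A mixed model for repeated measures on THI change at weeks 2, 4 and 6 would also do, with arm-by-visit terms, baseline THI and the stratification factors, and the week-6 contrast as primary. Specify one in advance: participants with only a baseline THI can be imputed but contribute no outcome to the mixed model.
2. **Sensitivity analysis.** Add control-based imputation or a tipping-point analysis, because missing at random cannot be tested.
3. **Mixed models.** State that no carried-forward values enter any of them.
4. **Definitions.** Name the primary analysis set, confirm that THI total is scored at weeks 2 and 4, and say how FA participants with only a baseline THI are handled.

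The cost is SAP wording and modest programming, with no extra visits if THI total is already scored at weeks 2 and 4. The price is a slightly more complex primary analysis resting on an untestable assumption, whose influence item 2 examines.
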